## List of Figures

Figure Number	Figure Description
14.2.4.1	Observed Mean MMSE by Visit (Safety Population)
14.2.4.2	Annualized Mean Change from Baseline in MMSE (Safety Population)
14.3.5.1.1	Box Plots of Hemoglobin by Visit – Conventional Units (Safety Population)
14.3.5.1.2	Box Plots of Hemoglobin Change from Baseline by Visit – Conventional Units (Safety Population)
14.3.5.1.3	Box Plots of Hemoglobin by Visit – SI Units (Safety Population)
14.3.5.1.4	Box Plots of Hemoglobin Change from Baseline by Visit – SI Units (Safety Population)
14.3.5.2.1	Box Plots of Reticulocytes by Visit – Conventional Units (Safety Population)
14.3.5.2.2	Box Plots of Reticulocytes Change from Baseline by Visit – Conventional Units (Safety Population)
14.3.5.2.3	Box Plots of Reticulocytes by Visit – SI Units (Safety Population)
14.3.5.2.4	Box Plots of Reticulocytes Change from Baseline by Visit – SI Units (Safety Population)
14.3.5.3.1	Box Plots of Neutrophils by Visit (Safety Population)
14.3.5.3.2	Box Plots of Neutrophils Change from Baseline by Visit (Safety Population)
14.3.5.4.1	Box Plots of Albumin by Visit – Conventional Units (Safety Population)
14.3.5.4.2	Box Plots of Albumin Change from Baseline by Visit – Conventional Units (Safety Population)
14.3.5.4.3	Box Plots of Albumin by Visit – SI Units (Safety Population)
14.3.3.4.4	Box Plots of Albumin Change from Baseline by Visit – SI Units (Safety Population)
14.3.5.5.1	Box Plots of ALT by Visit (Safety Population)
14.3.5.5.2	Box Plots of ALT Change from Baseline by Visit (Safety Population)
14.3.5.6.1	Box Plots of AST by Visit (Safety Population)
14.3.5.6.2	Box Plots of AST Change from Baseline by Visit (Safety Population)
14.3.5.7.1	Box Plots of Alkaline Phosphatase by Visit (Safety Population)
14.3.5.7.2	Box Plots of Alkaline Phosphatase Change from Baseline by Visit (Safety Population)

Figure Number	Figure Description
14.3.5.8.1	Box Plots of Total Bilirubin by Visit – Conventional Units (Safety Population)
14.3.5.8.2	Box Plots of Total Bilirubin Change from Baseline by Visit – Conventional Units (Safety Population)
14.3.5.8.3	Box Plots of Total Bilirubin by Visit – SI Units (Safety Population)
14.3.5.8.4	Box Plots of Total Bilirubin Change from Baseline by Visit – SI Units (Safety Population)
14.3.5.9.1	Box Plots of Direct Bilirubin by Visit – Conventional Units (Safety Population)
14.3.5.9.2	Box Plots of Direct Bilirubin Change from Baseline by Visit – Conventional Units (Safety Population)
14.3.5.9.3	Box Plots of Direct Bilirubin by Visit – SI Units (Safety Population)
14.3.5.9.4	Box Plots of Direct Bilirubin Change from Baseline by Visit – SI Units (Safety Population)

## List of Listings

Listing Number	Listing Description
16.2.1.1.1	Subjects Who Entered the Study (All Enrolled)
16.2.1.1.2	Informed Consent (All Enrolled)
16.2.1.1.3	Reconsent for Additional 12-Month Treatment Extension (All Enrolled)
16.2.1.2	Subject Disposition (All Enrolled)
16.2.1.3	Subject Visit Dates (All Enrolled)
16.2.2.1	Protocol Deviations (Safety Population)
16.2.2.2	Withdrawal of Consent (Safety Population)
16.2.2.3	Inclusion/Exclusion Criteria (Safety Population)
16.2.4.1	Demographics and Baseline Characteristics (Safety Population)
16.2.4.2	Medical History at Study Entry (Safety Population)
16.2.4.3.1	Prior Medications (Safety Population)
16.2.4.3.2	Concomitant Medications (Safety Population)
16.2.4.4	Procedures and Therapies (Safety Population)
16.2.5.1	Drug Accountability and Compliance (Safety Population)
16.2.5.2	By-Subject Summary of Overall Exposure (Safety Population)
16.2.5.3	Chronological Study Drug Administration Including Dose Interruption and Adjustment (Safety Population)
16.2.6.1	RUD Lite (Safety Population)
16.2.6.2.1	EQ-5D-5L (Safety Population)
16.2.6.2.2	EQ-5D-5L, Patient Rated (Safety Population)
16.2.6.2.3	EQ-5D-5L, Caregiver Rated (Safety Population)
16.2.7.1	Adverse Events (Safety Population)
16.2.7.2.1	Serious Adverse Events (Safety Population)
16.2.7.2.2	Fatal Adverse Events (Safety Population)
16.2.7.2.3	Non-Fatal Serious Adverse Events (Safety Population)
16.2.7.2.4	Serious Adverse Events (Additional Information About the SAE Collected on the AE CRF)
16.2.7.2.5	Serious Adverse Events (Collected on the SAE CRF)
16.2.7.3.1	Adverse Events Leading to Dose Reduction, Interruption or Study Drug Withdrawal (Safety Population)
16.2.7.3.2	All AEs for Subjects with Adverse Events Leading to Dose Reduction, Interruption or Study Drug Withdrawal (Safety Population)
16.2.7.4	Adverse Events of Special Interest (Safety Population)
16.2.8.1.1	Central Laboratory Normal Ranges (Safety Population)

Listing Number	Listing Description
16.2.8.1.2	Central Laboratory – Comments on Samples Not Analyzed (Safety Population)
16.2.8.2.1	Central Lab - Hematology – Conventional Units (Safety Population)
16.2.8.2.2	Central Lab - Hematology – SI Units (Safety Population)
16.2.8.2.3	Local Lab - Hematology – Conventional Units (Safety Population)
16.2.8.2.4	Local Lab - Hematology – SI Units (Safety Population)
16.2.8.3.1	Central Lab - Serum Chemistry – Conventional Units (Safety Population)
16.2.8.3.2	Central Lab - Serum Chemistry – SI Units (Safety Population)
16.2.8.3.3	Local Lab - Serum Chemistry – Conventional Units (Safety Population)
16.2.8.3.4	Local Lab - Serum Chemistry – SI Units (Safety Population)
16.2.8.4.1	Local Lab - Urinalysis – Conventional Units (Safety Population)
16.2.8.4.2	Local Lab - Urinalysis – SI Units (Safety Population)
16.2.8.5.1	Hematology Results of Potential Clinical Significance – Conventional Units (Safety Population)
16.2.8.5.2	Hematology Results of Potential Clinical Significance – SI Units (Safety Population)
16.2.8.5.3	Hematology Results of Potential Clinical Significance – Includes Only Hgb and Hct Reticulocytosis (Safety Population)
16.2.8.5.4	Hematology Results of Potential Clinical Significance – WBCs and Neutrophils (Safety Population)
16.2.8.5.5	Hematology Results of Potential Clinical Significance – Eosinophils (Safety Population)
16.2.8.5.6	Hematology Results of Potential Clinical Significance – Platelets (Safety Population)
16.2.8.6.1	Serum Chemistry Results of Potential Clinical Significance – Conventional Units (Safety Population)
16.2.8.6.2	Serum Chemistry Results of Potential Clinical Significance – SI Units (Safety Population)
16.2.8.6.3	Serum Chemistry Results of Potential Clinical Significance – Urea (Nitrogen) or Creatinine (Safety Population)
16.2.8.6.4	Serum Chemistry Results of Potential Clinical Significance – ALT, AST, GGT, Bilirubin or Alkaline Phosphatase (Safety Population)
16.2.9.1	Vital Signs (Safety Population)
16.2.9.2.1	Vital Sign Results of Potential Clinical Significance (Safety Population)
16.2.9.2.2	Subjects with Potentially Clinically Significant Vital Sign Results (Safety Population)
16.2.9.2.3	Respiratory Rate (Safety Population)

Listing Number	Listing Description
16.2.9.3	Pregnancy (Safety Population)
16.2.9.4	Physical Examination (Safety Population)
16.2.9.5	Neurological Examination (Safety Population)
16.2.9.6	Serotonin Toxicity Assessment (Safety Population)
16.2.9.7	Mini-Mental State Examination (MMSE) (Safety Population)
16.2.9.8.1	Central Electrocardiogram (Safety Population)
16.2.9.8.2	Local Electrocardiogram (Safety Population)

## **Appendix G: Table Layouts**

**Table 14.1.1.1  
Subject Disposition  
All Subjects**

	AD	bvFTD	All Subjects
Subjects Enrolled	n	n	n
Safety Population 	n (%)	n (%)	n (%)
Completed	n (%)	n (%)	n (%)
Discontinued	n (%)	n (%)	n (%)
All Reasons for Study Discontinuation 			
Reason 1	n (%)	n (%)	n (%)
Reason 2	n (%)	n (%)	n (%)
Primary Reason for Study Discontinuation 			
Reason 1	n (%)	n (%)	n (%)
Reason 2	n (%)	n (%)	n (%)
...			

All enrolled subjects who take at least one dose of study drug.

Subjects may be counted for more than one reason for study discontinuation but are counted only once for primary reason for discontinuation.

Note: The following xx subjects vvv, www, xxx, yyy, zzz were enrolled but not dosed. (programming note: List the subject IDs)

*Programming Note: Repeat table for Table 14.1.1.4 Subject Disposition – Non-AChEI/Memantine Users (All Subjects)*

**Table 14.1.1.2**  
**Subject Disposition by Region**  
**All Subjects**

	AD	bvFTD	All Subjects
Subjects Enrolled	n	n	n
Safety Population 	n (%)	n (%)	n (%)
Completed	n (%)	n (%)	n (%)
Discontinued	n (%)	n (%)	n (%)
All Reasons for Study Discontinuation 			
Reason 1	n (%)	n (%)	n (%)
Reason 2	n (%)	n (%)	n (%)
Primary Reason for Study Discontinuation 			
Reason 1	n (%)	n (%)	n (%)
Reason 2	n (%)	n (%)	n (%)
...			

All enrolled subjects who take at least one dose of study drug.

 Subjects may be counted for more than one reason for study discontinuation but are counted only once for primary reason for discontinuation.

Note: The following xx subjects vvv, www, xxx, yyy, zzz were enrolled but not dosed. (programming note: List the subject IDs)

**Table 14.1.1.3**  
**Subject Disposition by Country and Site**  
**All Subjects**

Country	Site		AD	bvFTD	All Subjects
Country 1	All Sites	Subjects Enrolled	n	n	n
		Safety Population 	n (%)	n (%)	n (%)
		Completed	n (%)	n (%)	n (%)
		Discontinued	n (%)	n (%)	n (%)
		All Reasons for Study Discontinuation 			
		Reason 1	n (%)	n (%)	n (%)
		Reason 2	n (%)	n (%)	n (%)
		Primary Reason for Study Discontinuation 			
		Reason 1	n (%)	n (%)	n (%)
		Reason 2	n (%)	n (%)	n (%)
		...			
		Site 1			
		...			
		...	...		

All enrolled subjects who take at least one dose of study drug.

 Subjects may be counted for more than one reason for study discontinuation but are counted only once for primary reason for discontinuation.

Note: The following xx subjects vvv, www, xxx, yyy, zzz were enrolled but not dosed. (programming note: List the subject IDs)

*Programmer note: Start each site on a new page. Group sites within country within region.*

**Table 14.1.2.1**  
**Study Discontinuation by Time Period**  
**Safety Population**

	AD (N= )	bvFTD (N= )	All Subjects (N= )
Study Discontinuation	n (%)	n (%)	n (%)
Study Discontinuation on Day 1	n (%)	n (%)	n (%)
Reason 1	n (%)	n (%)	n (%)
Reason 2	n (%)	n (%)	n (%)
...			
Study Discontinuation During Days 2-	n (%)	n (%)	n (%)
Reason 1	n (%)	n (%)	n (%)
Reason 2	n (%)	n (%)	n (%)
...			
...			
Repeat for other period categories			
...			

Note: Percentages are based on the number of subjects in the Safety Population.

*Programming Note: Repeat table for Table 14.1.2.2 Study Discontinuation by Time Period – Non-AChEI/Memantine Users (Safety Population)*

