4 STUDY DESIGN

4.1 General Description

This study is a multicenter, open-label extension study of LMTM in subjects with mild to moderate AD or bvFTD at the time they first enrolled in a double-blind trial.

Participation in this study will be offered to any subject who completed participation in a TauRx-sponsored Phase 2 or Phase 3 double-blind study, *i.e.*, Studies TRx-237-005, TRx-237-007, TRx-237-008, or TRx-237-015. Only AD subjects who have completed the full double-blind period of the originating studies (including the 1-month post-treatment follow-up), or bvFTD subjects who completed the full double-blind treatment period through Visit 9 in TRx-237-007, will be eligible for inclusion in this open-label extension study (see Section 6.2.1 for guidance regarding study drug dosing for bvFTD subjects entering this extension study).

Subjects may enter this study at the final designated visit in the double-blind study, provided subjects and caregivers have had sufficient time to consider the study prior to giving consent, or at any subsequent time. Subjects may continue participation at the same site at which they participated in the originating double-blind study or transfer to a geographically close investigational site (that also participated in the same study). Eligibility for continued open-label treatment is to be determined by the original investigator and, if applicable, a referral to a new site made. The new investigator will have access to the subject's prior study eCRFs and is to confirm eligibility (see Section 5); Baseline testing can be repeated as necessary in the judgment of the new investigator. The initial visit will be designated Visit 1.

The initial LMTM dose is 200 mg/day (one 100-mg tablet twice daily [*b.i.d.*]). The dose may be increased (at Visit 3 or at any subsequent dispensing visit as determined by the investigator during the treatment period) to a maximum of 300 mg/day (or in those countries where limited by a CA or EC, 200 mg/day) in response to benefit as judged by the investigator. Alternatively, the dose may be interrupted at any time (for up to 30 days on a given occasion) or decreased to a minimum of 100 mg/day (at any time at or after Visit 2) as needed in response to safety assessments (see Section 6.2.2). The recommended decrement or increment of dose adjustment is 100 mg/day. The study drug will be dispensed in 13-week (\pm 2-week) supplies.

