4.3 Duration

The study will continue until alternate options for access to treatment are available, *i.e.*, commercialization or, depending on country, on a Named Patient or compassionate basis, or availability *via* a Managed Access Program. (See Section 5.4 for a discussion of other reasons for study termination.)

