5.3 Discontinuation/Withdrawal

For a discussion of reasons for dose adjustment or permanent discontinuation of study medication on the basis of safety, see Section 6.2.3. These include clinically evident hemolytic anemia (Section 6.2.3.1), serotonin syndrome (Section 6.2.3.2), prolongation of the QT interval on ECG and decrease in renal function (Section 6.2.3.3).

Subjects may discontinue study drug and withdraw (drop out) from the study at any time for any reason. The caregiver may also withdraw his or her consent at any time for any reason. If a caregiver withdraws his or her consent, the subject must then also be withdrawn if alternative arrangements are not available (*e.g.*, an alternate caregiver). Furthermore, the investigator also has the right to discontinue trial medication if he or she judges that treatment is no longer appropriate, the subject's clinical condition is worsening, or for an adverse event.

At the completion of each 12-month period of open-label treatment, the principal investigator must determine whether or not continued treatment is warranted on the basis of continued benefit and safety and tolerability profile. If eligible, the subject and/or caregiver must give informed consent for continued participation. In Germany and the Netherlands, continuation of treatment is not permitted if the subject is unable to give consent.

If study drug is discontinued or the subject/caregiver elect(s) not to re-enroll in a subsequent open-label treatment phase, the reason should be recorded as one of the following:

- AE
- Death
- Lack of efficacy (including progressive disease or worsening of cognitive capacity; in Germany, this includes loss of the ability to give consent if the legal representative or caregiver is not available or does not agree to continued participation)
- Lost to follow up
- Withdrawal by subject or legal representative (or caregiver), including specific reasons wherever possible
- Protocol deviation
- Non-compliance with study drug
- Pregnancy
- Study terminated by Sponsor
- Physician decision, including specific reason(s) wherever possible

- Other (specify)

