## 5.2 Subject Disposition

Subject disposition information will be summarized for all subjects, overall and by region, country and site. Summaries will include: the number of subjects, (discontinued or completed), all reasons for discontinuation, and the primary reason for discontinuation.

The timing of the early discontinuations will be assessed by summarizing discontinuations by reason during each of the following time periods, overall and by region:

- Day 1
- Days 2 - 53
- Days 54 - 137
- Days 138 - 228
- Days 229 - 319
- Days 320 - 410
- Days 411 - 501
- Days 502 - 591
- Days 592 - 683
- > 683 Days

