**Table 14.1.2.3**  
**Study Discontinuation by Time Period and by Region**  
**Safety Population**

Country		AD (N= )	bvFTD (N= )	All Subjects (N= )
Country 1	Study Discontinuation	n (%)	n (%)	n (%)
	Study Discontinuation on Day 1	n (%)	n (%)	n (%)
	Reason 1	n (%)	n (%)	n (%)
	Reason 2	n (%)	n (%)	n (%)
	...			
	Study Discontinuation During Days 2-	n (%)	n (%)	n (%)
	Reason 1	n (%)	n (%)	n (%)
	Reason 2	n (%)	n (%)	n (%)
	...			
	...			
	Repeat for other period categories			
	...			
...				

Note: Percentages are based on the number of subjects in the Safety Population.

**Table 14.1.3.1  
Protocol Deviations  
Safety Population**

	AD (N= )	bvFTD (N= )	All Subjects (N= )
All Deviations Types	n (%)	n (%)	n (%)
Informed consent	n (%)	n (%)	n (%)
Safety	n (%)	n (%)	n (%)
IP / Treatment Deviation	n (%)	n (%)	n (%)
Other Deviations	n (%)	n (%)	n (%)

Note: IP = investigational product

path\t\_program.sas date time

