**Table 14.3.1.1**  
**Study Drug Exposure and Compliance**  
**Safety Population**

	AD (N= )	bvFTD (N= )	All Subjects (N= )
Total Duration of Exposure (days) 			
n	n	n	n
Mean (SD)	xx.x (xx.xx)	xx.x (xx.xx)	xx.x (xx.xx)
Median	xx.x	xx.x	xx.x
Min, Max	xx, xx	xx, xx	xx, xx
Total Duration Category (days) 			
1	n (%) [n (%)]	n (%) [n (%)]	n (%) [n (%)]
2-	n (%) [n (%)]	n (%) [n (%)]	n (%) [n (%)]
etc. (refer to Section 5.2)			
Duration of the Exposure Accounting for Interruptions (days) 			
n	n	n	n
Mean (SD)	xx.x (xx.xx)	xx.x (xx.xx)	xx.x (xx.xx)
Median	xx.x	xx.x	xx.x
Min, Max	xx, xx	xx, xx	xx, xx
Mean Daily Dose (mg) 			
n	n	n	n
Mean (SD)	xx.x (xx.xx)	xx.x (xx.xx)	xx.x (xx.xx)
Median	xx.x	xx.x	xx.x
Min, Max	xx, xx	xx, xx	xx, xx

 Total duration of exposure in days is defined as the difference between the last dose date recorded on the study exit CRF page and the first dose date, plus 1 day.

 Number (%) of subjects in each category followed by [cumulative number (%) of subjects].

 Defined as the difference between the last dose date recorded on the study exit CRF page and the first dose date, minus the duration of dose interruption(s), plus 1 day.

 Defined as the total dose received divided by total duration of exposure.

 Defined as 100 x (Total Tablets Dispensed – Total Tablets Returned) / (Expected Number of Tablets).

path\t\_program.sas date time

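### Dropout-timing tables divide every period by the full Safety Population, so from Day 138 to Day 683 the percentages for non-administrative reasons fall even at constant risk; add numbers on study and person-time rates or a Kaplan-Meier curve

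*SAP*

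**What the plan says.** SAP 5.2 (Subject Disposition) sets the purpose: "The timing of the early discontinuations will be assessed by summarizing discontinuations by reason" in ten periods, overall and by region. The periods are Day 1; Days 2-53; 54-137; 138-228; 229-319; 320-410; 411-501; 502-591; 592-683; and beyond Day 683.

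The shells for Tables 14.1.2.1 and 14.1.2.3 both carry the footnote "Note: Percentages are based on the number of subjects in the Safety Population". Table 14.1.2.2 (non-AChEI/memantine users) repeats the first shell. None of the three has a row for the number still on study. Appendix F lists no discontinuation rate by period and no time-to-discontinuation figure.

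Follow-up differs between subjects by design. Protocol 4.1 lets subjects enter at the final double-blind visit, given enough time "to consider the study prior to giving consent, or at any subsequent time". Protocol 4.3 sets no fixed end: "The study will continue until alternate options for access to treatment are available". Protocol 5.3 includes "Study terminated by Sponsor" among the reasons for stopping, so administrative closure can be separated from the other reasons.

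Related information appears elsewhere. Table 14.3.1.1 gives cumulative exposure-duration categories on the same cut-points ("etc. (refer to Section 5.2"), plus total subject-years. The Appendix A visit windows after Day 1 match the SAP 5.2 periods, and the by-visit laboratory and vital-sign tables print n for each window.

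**The concern.** A question about timing is a question about risk among those still present. With a fixed denominator, the percentage for a period mixes that risk with the share of subjects who remain and have had time to reach the period. That share shrinks in two ways: subjects leave, and late entrants are cut off by closure or data cut-off. Each pulls later percentages down without any change in tolerability.

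Long-term safety and tolerability is a primary objective, and these are the tables that the SAP names for dropout timing. Read at face value, they could suggest that dropout eases with longer treatment when the risk has not changed.

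**Working it through.** **Plan's own figure.** There is none to reproduce. The documents state no discontinuation rate for this extension, no entry dates and no closure date.

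**Inputs.**
- Period limits from SAP 5.2. The six periods from Day 138 to Day 683 last 91, 91, 91, 91, 90 and 92 days.
- Month = 30.4375 days and year = 365.25 days (SAP 4.2).
- Base case (assumed): entry uniform over 24 months, closure at month 30, constant hazard h = 0.30 per year for non-administrative discontinuation. Potential follow-up is then uniform between 6 and 30 months.
- Hazard range (assumed): 0.15 to 0.50 per year. As a plausibility check, the Protocol synopsis assumes 60 to 80% completion of the double-blind studies, and Protocol 2 gives 12 to 18 months of treatment. These imply -ln(0.8)/1.5 = 0.149 to -ln(0.6)/1.0 = 0.511 per year.

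**Formulas.** Let S(t) = exp(-ht), and let F(t) be the share of subjects whose potential follow-up exceeds t.
- Tabulated percentage for Days a to b = integral of h S(t) F(t) from a-1 to b.
- Share on study at the start of the period = S(a-1) F(a-1).
- Rate = tabulated fraction divided by subject-years per subject in the period.

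**Simultaneous entry (depletion alone, F = 1).**
- Days 138-228: exp(-0.30 × 137/365.25) - exp(-0.30 × 228/365.25) = 0.8936 - 0.8292 = 6.44%.
- Days 592-683: exp(-0.30 × 591/365.25) - exp(-0.30 × 683/365.25) = 0.6154 - 0.5706 = 4.48%.

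**Base case.** At Day 591, F = (913.125 - 591)/730.5 = 0.441, so 0.6154 × 0.441 = 27.1% are still on study. In the last column the hazard rises to 0.45 from Day 411.

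| Days | On study at start (%) | SAP percentage, constant risk | Rate per 100 subject-years | SAP percentage, hazard 0.45 from Day 411 |
|---|---|---|---|---|
| 138-228 | 89.4 | 6.34 | 30 | 6.3 |
| 229-319 | 77.8 | 5.23 | 30 | 5.2 |
| 320-410 | 62.6 | 4.17 | 30 | 4.2 |
| 411-501 | 49.2 | 3.23 | 30 | 4.8 |
| 502-591 | 37.4 | 2.38 | 30 | 3.4 |
| 592-683 | 27.1 | 1.70 | 30 | 2.3 |

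**Range at constant risk, Days 138-228 to Days 592-683.**
- Entry over 12 months: 6.44 to 3.39%.
- Closure at month 36: 6.44 to 2.82%.
- Hazard 0.15: 3.41 to 1.10%.
- Hazard 0.50: 9.57 to 2.00%.

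**Hazard rising by half from Day 411, other scenarios.** The six percentages are:
- closure at month 36: 6.4, 6.0, 5.5, 6.6, 5.0, 3.9;
- entry over 12 months: 6.4, 6.0, 5.5, 7.6, 6.5, 4.6;
- simultaneous entry: 6.4, 6.0, 5.5, 7.6, 6.7, 6.1.

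The rate reads 30, 30, 30, 45, 45, 45 in every scenario.

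**Periods outside Days 138-683.** The first three last 1, 52 and 84 days, so their percentages grow with width alone. The last is open-ended. At constant risk, from Days 592-683 to beyond Day 683, the percentage goes from 1.7 to 1.6% (base), 3.4 to 3.2% (12-month entry), 2.8 to 4.9% (closure at month 36) and 4.5 to 9.8% (simultaneous entry, closure at month 30). None of these periods can be compared with the six in the middle.

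**The case against.** A fixed, disclosed denominator is a legitimate convention for disposition tables. Period rows then add up to the overall discontinuation row, and nothing is mislabelled. That stands, and it is why the fixed percentages should stay.

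Numbers remaining are not wholly hidden. They can be approximated from Table 14.3.1.1 by diagnosis, from its repeat for non-AChEI/memantine users, and from the n in the by-visit tables. This also stands, with limits. Table 14.3.1.1 counts to the last dose, neither source is planned by region, subject-years are given only in total, and no rate by period is planned anywhere.

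Constant hazard is a simplification. Continuation is reconsidered about every 12 months, so a cluster of exits within Days 320-410 is plausible. The scenarios show how the denominator behaves. They do not predict dropout in this study.

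A reader might infer more than the documents support:
- That the tables would conceal a rise in risk. They would not conceal it entirely: in all four rising-hazard scenarios the percentage goes up in Days 411-501. What is lost is that the risk stays high afterwards.
- That percentages fall in every later period. The one beyond Day 683 can rise.
- That the counts are wrong, or that the true pattern is less favourable. Nothing in the documents shows either.

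The SAP also leaves open which date places a subject in a period and whether subjects on treatment at closure count as completed. Table 14.1.2.3 is titled by region but has a country row heading. These are missing detail or clerical slips, and the point does not rest on them.

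**Conclusion.** The point holds for non-administrative reasons over Days 138-683. Under every scenario tried with a constant hazard, the first-to-last percentage falls. The smallest fall at 0.30 per year is 6.4 to 4.5%, from depletion alone, and the base case gives 6.3 to 1.7%, with an unchanged 30 per 100 subject-years. These sizes rest on assumed entry, closure and hazard. The direction needs only that subjects leave or have unequal follow-up while the risk stays about constant at rates of this order.

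The counts are a valid description, and no primary conclusion or planned comparison depends on the percentages. This is a worthwhile improvement in presentation, because the tables as laid out do not answer the timing question that SAP 5.2 sets for them.

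**What to change.** Keep the counts and the fixed-denominator percentages. In Tables 14.1.2.1 to 14.1.2.3, add for each period:
- the number still on study at its start;
- non-administrative discontinuations per 100 subject-years within the period, in total and by reason.

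In addition, or instead of the rates, plot a Kaplan-Meier curve of time to any non-administrative discontinuation, overall and by region, censoring at sponsor termination, study closure or data cut-off. If curves by reason are shown, use cumulative incidence, because the reasons compete.

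Dividing by the number on study at the start of each period is a weaker remedy under staggered entry. In the base case that percentage still drifts from 7.09 to 6.25% at constant risk. The person-time rate does not drift, and it also copes with unequal and open-ended periods.

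These are descriptive summaries, so they fit Protocol 9.3.2, which plans no inferential statistics. The cost is a few lines in SAP 5.2, including the date that ends a subject's time on study, and modest extra programming with dates already planned for Listing 16.2.1.2.
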